9.4.2.4 Surgical Prophylaxis

Efficacy of *Octafibrin* in surgical prophylaxis will be assessed intra-operatively (at the end of surgery = after last suture) by the surgeon and post-operatively by the haematologist using two 4-point efficacy scales. In the event that any intra- or post-operative endpoint data differ between the investigator's assessment and the adjudicated assessment by the IDMEAC, the endpoint will be that based on the adjudicated assessments. The efficacy of *Octafibrin* in surgical prophylaxis will be evaluated by descriptive statistics based on an overall assessment.

The IDMEAC will conduct an independent adjudication of all haemostatic efficacy results and adjudicate the investigator's assessments of the intra- and post-operative assessments ('secondary adjudication').

The primary endpoint ('success' or 'failure') will be derived from the adjudicated intra- and post-operative assessments according to the agreed algorithm presented in Table 6.

Table 6: Algorithm for the adjudicated intra- and post-operative assessments of haemostatic efficacy

Intra-operative	Post-operative assessment				
assessment	Excellent	Good	Moderate	None	
Excellent	Success	Success	Success	Primary adjudication	
Good	Success	Success	Primary adjudication	Failure	
Moderate	Success	Primary adjudication	Failure	Failure	
None	Primary adjudication	Failure	Failure	Failure	

Outcomes indicated 'IDMEAC' will be assigned following adjudication by the IDMEAC ('primary adjudication').

9.4.2.5 Safety Analysis Plan

The analysis of safety will be based on the safety population.

All AEs (including events likely to be related to the underlying disease, or a concomitant illness or medication or clinically significant abnormalities in laboratory parameters or vital signs) will be displayed in summary tables and listings.

Incidences of AEs will be given as numbers and percentages of subjects with:

- Any AE.
- Any SAE.
- Any AE probably or possibly related to the IMP.
- Any AE temporally related (within 24 hours after end of infusion) to the IMP.
- Any severe AE.
- Any withdrawal due to AE.
- Any AE by Medical Dictionary for Regulatory Activities (MedDRA) preferred term (descending frequency).
- Any AE temporally related (within 24 hours after end of infusion) by MedDRA preferred term (descending frequency).
- Any AE by MedDRA system organ class (SOC).
- Any AE temporally related (within 24 hours after end of infusion) by MedDRA SOC.

Summary tables for AEs will be given by SOC and preferred term. Additionally, AEs will be summarised by severity and relationship to the IMP.

The MedDRA coded terms and the corresponding original (verbatim) terms used by the investigator will be listed.

For laboratory variables (analyses of haematology, biochemistry, and thrombogenicity), the mean, standard deviation, median, and range will be presented. Laboratory variables will also be presented graphically. Intra-individual changes between pre-infusion and the respective post-infusion time points will be analysed using shift tables and graphical presentations. Physical examination data will be presented in frequency tables.

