3.2 Overall Study Design and Plan

This is a multinational, multi-centre, prospective, open-label, uncontrolled, Phase III study to assess the efficacy and safety of *Octafibrin* for on-demand treatment of acute bleeding and surgical prophylaxis in subjects with congenital fibrinogen deficiency.

A total of 24 male and female subjects with congenital fibrinogen deficiency will be enrolled in the study. This will include at least 4 subjects aged between 12 and 18 years (only 18 and above in Russia). This will also include at least 4 surgeries, 2 of which should be performed in subjects aged between 12 and 18 years (only 18 and above in Russia). The study will be conducted in approximately 15 study centres worldwide.

During the study observation period, enrolled patients will be treated for any bleeding episodes or planned surgeries that can be managed under the protocol. Patients may remain in the study until the 24th patient has at least one documented bleeding episode. The study will be considered completed when a minimum of 24 subjects have at least one documented bleeding episode. The study as a whole should be completed within 5 years.

As many bleeding episodes or surgeries as possible occurring throughout the study observation period will be documented. Only the first bleeding episodes will be used for the analysis of the primary endpoint. All bleeding episodes documented in the study will be assessed as a secondary endpoint.

The investigator will inform the monitor of any recruitment difficulty or delay of the anticipated completion date.

Patients should be treated with the investigational medicinal product (IMP) whenever possible. If, in the opinion of the investigator, a bleeding episode is not effectively stopped or surgical prophylaxis is not adequate after the recommended dose of *Octafibrin* has been administered, the subject may receive a different licensed fibrinogen concentrate (e.g., Haemocomplettan P®/RiaSTAPTM) or whatever the investigator considers standard of care. The use of another licensed fibrinogen concentrate is also permitted in emergency situations, e.g., if the IMP is not available for the patient in time.

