3.2.1 On-demand Treatment of Acute Bleeding

Subjects presenting to the study site for on-demand treatment of an acute bleeding episode who are eligible for enrolment and have provided written informed consent will be included into the study.

Each subject will receive at least 1 infusion of *Octafibrin* for the treatment of acute bleeding on Day 1. The individual **subject observation and follow-up period** for each documented episode starts with the first dose of *Octafibrin* administered for on-demand treatment of an acute bleeding episode (Day 1) and will be followed for up to Day 30.

Each subject's **treatment observation period** is defined according to the severity of the event and will last at least 3 days for minor and 7 days for major bleeding episodes.

On each day of the treatment observation period (i.e., 3 days for minor and 7 days for major bleeding), fibrinogen plasma levels will be measured daily to determine whether additional infusions of *Octafibrin* are needed:

- Additional infusions of *Octafibrin* **should** be administered if the actual fibrinogen plasma level measured on these days is below the accepted lower limit of the target level (80 mg/dL for minor bleeding, 130 mg/dL for major bleeding).
- If the actual fibrinogen plasma level is above the accepted lower limit of the target level, *Octafibrin* **should not** be administered.

The actual treatment duration will be determined by the investigator based on his/her judgement of the subject's condition.

All adverse events (AEs), including thromboembolic events and early signs of allergic or hypersensitivity reactions, occurring between the start of the first *Octafibrin* infusion and the end of each 30-day observation and follow-up period will be recorded. Concomitant medications will also be recorded throughout each 30-day observation and follow-up period.

All SAEs occurring after the first IMP infusion will be documented and reported for a patient throughout the duration of the patient's participation in the study or as required to meet local regulations. Also, any concomitant medications used to treat an SAE will be recorded.

At the end of the study (i.e., when the 24th patient has had at least one treated bleeding episode), all patients will be asked to return for a Study Completion Visit.

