3.3 Discussion of Study Design and Choice of Control Group(s)

As there are currently no guidelines concerning fibrinogen concentrates in either the US or the EU, the study was designed following established programs for Factor IX concentrates.

Typically, the clinical evaluation of a new concentrate initially examines the IVR and the PK properties of the principal active factor. Prior to initiating the present study, comparative PK data have been obtained in study FORMA-01.

The open-label uncontrolled design and choice of study objectives are motivated by regulatory requirements for Factor IX [14] and discussions with the regulatory bodies.

The median response value used in the fibrinogen dosage calculation is the median incremental in vivo recovery reported in the interim analysis of study FORMA-01.

Although all bleeding episodes occurring throughout the study observation period will be documented, only the first bleeding episode per patient will be used for the analysis of the primary endpoint (see Section 3.1.1). This is because the study will end once the 24th enrolled patient has at least one documented bleeding episode, potentially resulting in a large diversity in the number of bleeding episodes between patients. The entirety of bleeding episodes documented in the study will be assessed as a secondary endpoint (see Section 3.1.2).

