5.8 Assessment of Treatment Compliance

Treatment compliance will be measured in terms of the subject receiving an infusion of *Octafibrin* from the study personnel. Administered doses of *Octafibrin* will be recorded for every infusion, including dates, times, and batch numbers; the batch numbers will be reported in the final study report.

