1 INTRODUCTION

This Statistical Analysis Plan (SAP) provides a comprehensive and detailed description of statistical methods to be used to analyze the data for protocol FORMA-02, Version 6.0, 31-Oct-2014, as amended on 08-July-2016 (Version 7.0).

The purpose of this SAP is to outline the planned analyses to be completed to support the completion of the Clinical Study Report (CSR) for protocol FORMA-02. In addition, this SAP will describe any clarifications or modifications to the endpoints and statistical methods in the protocol. The planned analyses identified in this SAP will supersede the statistical sections in protocol and will be included in regulatory submissions and/or future manuscripts. In addition, exploratory analyses not necessarily identified in this SAP may be performed to support the clinical development program. Additional exploratory analyses may be added as addendums to this SAP after the signoff. Any post-hoc, or unplanned, analyses not identified in this SAP performed will be clearly identified in the respective CSR.

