9 SAFETY ANALYSES

AEs and SAEs will be coded by latest version 17 or higher of MedDRA body system and preferred term, and tabulated by indicating number and percentage of subjects and number of events. Number and percentage of subjects who experience any Adverse Drug Reaction (ADR) will be summarized.

AEs will be collected and evaluated for relation to test article, seriousness, intensity, frequency, measures taken and outcome.

Descriptive statistics and subject listing will be presented for concomitant medications.

The analysis of safety will be based on the safety population.

All AEs occurring after initiation of study treatments (including events likely to be related to the underlying disease, or a concomitant illness or medication or clinical significant abnormalities in laboratory parameters or vital signs) will be displayed in summary tables and listings.

Treatment emergent AEs will be those occurring during infusion or in the 45-day observation period after the first infusion. ADRs will be classified by the Sponsor as either expected or unexpected

FORMA-02	JSS Medical Research - Data Management		
Statistical Analysis Plan			
Form Number: MNI-DM-BIS-01 v 6.0-T1	Current Version Number: 2.0	Previous Version Number: 1.1 9-April-2015	Date: 11-July-2016

Incidences of AEs will be given as numbers and percentages of subjects with:

- Any AE.
- Any SAE.
- Any AE probably or possibly related to the IMP.
- Any AE temporally related (within 24 hours after end of infusion) to the IMP.
- Any severe AE.
- Any withdrawal due to AE.
- Any AE by Medical Dictionary for Regulatory Activities (MedDRA) preferred term (descending frequency).
- Any AE temporally related (within 24 hours after end of infusion) by MedDRA preferred term (descending frequency).
- Any AE by MedDRA system organ class (SOC).
- Any AE temporally related (within 24 hours after end of infusion) by MedDRA SOC.

Summary tables for AEs will be given by SOC and preferred term. Additionally, AEs will be summarized by severity and relationship to the IMP.

The MedDRA coded terms and the corresponding original (verbatim) terms used by the investigator will be listed.

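### SAP 9 counts subjects with AEs and AE events but plans no AE rate per infusion or per treated episode, although exposure per subject is expected to vary widely

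*Protocol*

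**What the plan says.** Protocol 9.4.2.5 introduces its AE summary with "Incidences of AEs will be given as numbers and percentages of subjects with" and then lists rows such as any AE, any SAE, related AEs and AEs in the 24 hours following an infusion. SAP 9 repeats the list and adds that AEs and SAEs are "tabulated by indicating number and percentage of subjects and number of events". The SAP governs: "The planned analyses identified in this SAP will supersede the statistical sections in protocol" (SAP 1).

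On exposure, Protocol 3.2 sets no limit: "As many bleeding episodes or surgeries as possible occurring throughout the study observation period will be documented". Protocol 3.3 foresees the consequence, "potentially resulting in a large diversity in the number of bleeding episodes between patients", and gives it as the reason for confining the primary endpoint to each patient's first bleed. For bleeds, Protocol 3.2.1 collects AEs from the start of the first infusion, and those up to "the end of each 30-day observation and follow-up period will be recorded". For surgery, collection stops at the Last Post-Operative Day (Protocol 7.4). SAEs are collected throughout participation after the first infusion and labelled as falling in an active or an inactive period (Protocol 7.5). Under Protocol 5.8, administered doses "will be recorded for every infusion, including dates, times, and batch numbers".

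SAP 9 also defines a treatment-emergent window: "Treatment emergent AEs will be those occurring during infusion or in the 45-day observation period after the first infusion".

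**The concern.** A subject treated for ten bleeds has ten AE windows, and a subject treated for one bleed has one. Both count once in the denominator of every percentage row. The percentage depends on how risky each use is and on how many uses there were, and the table alone cannot separate the two. The rows for AEs in the 24 hours after an infusion show this most clearly: they concern something that happens per infusion, yet the denominator is subjects.

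The study is pivotal and has no control arm, so no concurrent group with similar exposure helps the reader interpret the figure. A reader who wants the AE risk of one infusion or one treated bleed would have to build the ratio, choosing the denominator and the rule for assigning events after the data are known.

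**Working it through.** **What is planned, side by side**

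- Numerators: subjects with an event, and the number of events (SAP 9).
- Denominator: subjects. No AE row in either document uses infusions, treated bleeds, surgeries or time at risk.
- Exposure: infusion frequency and treatment duration are summarised under Octafibrin use (Protocol 9.4.3, SAP 8.3.1). That summary is not linked to AEs. Its dose summary names minor and major bleeds and does not mention surgery.
- Efficacy has both a first-bleed analysis and an all-bleeds analysis (SAP 8.1 and 8.3.4). Safety has only the pooled rows.

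**Illustration of size**

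The documents state no expected AE rate and no distribution of episodes, so there is no figure of the plan to reproduce. Both inputs below are assumptions. Let q be the AE risk per treated episode, equal and independent across episodes, and k the number of episodes. A subject's chance of at least one AE is 1 − (1 − q)^k. For q = 0.05 and k = 5 this is 1 − 0.95^5 = 0.226.

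| q | k = 1 | k = 2 | k = 5 | k = 10 |
|---|---|---|---|---|
| 2% | 2.0% | 4.0% | 9.6% | 18.3% |
| 5% | 5.0% | 9.8% | 22.6% | 40.1% |
| 10% | 10.0% | 19.0% | 41.0% | 65.1% |

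These are chances for one subject. For a study-level figure, average over 24 subjects, the planned minimum, under three assumed patterns:

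- A: 1 episode each (24 episodes).
- B: 12 subjects with 1, 4 with 2, 4 with 4 and 4 with 10 (12 + 8 + 16 + 40 = 76 episodes).
- C: 4 episodes each (96 episodes).

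Pattern B at q = 5%: (12 × 0.0500 + 4 × 0.0975 + 4 × 0.1855 + 4 × 0.4013) / 24 = 3.337 / 24 = 13.9%.

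| q | A | B | C | Per 100 episodes, all patterns |
|---|---|---|---|---|
| 2% | 2.0% | 6.0% | 7.8% | 2 |
| 5% | 5.0% | 13.9% | 18.5% | 5 |
| 10% | 10.0% | 24.8% | 34.4% | 10 |

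At q = 5% the percentage of subjects varies by a factor of 18.5 / 5.0 = 3.7 while the risk per episode is unchanged.

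**Sensitivity to the assumption**

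Independence gives a large rise. At the other extreme, suppose 5% of subjects always have an AE and the rest never do. The percentage is then 5% whatever k is. Between these two cases, the figure for k = 10 and a 5% risk per episode runs from 5% to 40%.

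**Are the numerators defined?**

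The SAP's 45-day window is counted from the first infusion, without saying whether that means the first in the study or the first in the episode. Protocol 7.4 and 7.4.1.2 use 30 days for each treated bleed, and SAP 4.3.1 itself follows each documented bleed up to Day 30. If the first infusion in the study is meant, AEs in a bleed that starts after day 45 would not be treatment-emergent unless they occurred during an infusion. The SAP is written for Protocol version 7.0 and the Protocol reviewed here is version 6.0, but the mismatch with SAP 4.3.1 lies within the SAP.

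**The case against.** The percentage of subjects is a standard descriptive measure. Safety analysis is descriptive only (Protocol 9.2), with no hypothesis or decision rule attached. The subgroups in SAP 6.1.2 are not tied to AE tables, and no cross-study comparison is planned. All of this stands, and it is why the existing rows are not an error.

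Much of the information will also be reported. SAP 9 gives event counts, SAP 8.3.1 summarises infusion frequency, and SAP 11 lists all CRF data. A reader could form a crude overall rate. This stands in part: the ratio is not pre-specified, surgical infusions are not clearly covered, and a count can be dominated by one frequently treated subject.

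The illustration assumes equal, independent risks. That also stands: if AEs cluster in susceptible subjects, the percentage rises less or not at all.

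A reader might infer more than the documents support:

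- *AEs are reported only as a percentage of subjects.* The governing SAP adds the number of events.
- *The tables show how often people bled instead of the product's risk.* The percentage mixes the two and does not replace one with the other.
- *Confining the primary endpoint to first bleeds makes all-episode safety tables inconsistent.* That restriction serves the endpoint carrying the hypothesis test, and efficacy over all bleeds is reported as well.

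Rates per episode have difficulties of their own. AE windows differ between bleeds and surgery. A new, unrelated bleed between Day 14 and Day 30 postpones the Day 30 evaluations (Protocol 6.1.2.5), so windows can overlap. Inactive-period SAEs belong to no episode. Any added rate has to deal with these.

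**Conclusion.** The gap is real but limited. No AE rate per infusion or per treated episode is pre-specified, in a study where exposure per subject is uncapped and expected to be very uneven. In the assumed 24-subject patterns, the percentage of subjects with an AE differs almost fourfold at a constant 5% risk per episode. That size depends on independent, equal risks and on invented episode counts, and it could be nil if AEs cluster in a few subjects. The 40% for ten episodes describes one such subject and should not be read as a likely study incidence.

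This is a cheap improvement to the reporting, and the planned tables are not wrong. The two treatment-emergent and follow-up windows need reconciling in any case, because they determine which events count.

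**What to change.** Keep the existing rows in SAP 9 and add:

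- (a) AEs in the 24 hours after the end of an infusion, as events per infusion.
- (b) Any AE, related AEs and active-period SAEs per treated bleed, split by minor and major, and separately per surgery because the AE windows differ. Assign each event to the most recent treated episode, and report inactive-period SAEs on their own.
- (c) The percentage of subjects with an AE in their first treated bleed. This is the episode the primary endpoint uses. The first treated episode of any kind could be a surgery and would not match it.

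Reconcile the 45-day treatment-emergent window in SAP 9 with the 30-day window per bleed in the Protocol and SAP 4.3.1, and state which infusion starts the clock.

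The cost is a few table rows and one attribution rule in the SAP. Infusion dates and times are already recorded, so no new data or change in procedures is needed.

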9.4.3 Additional Analyses

Octafibrin use

Octafibrin will be individually dosed to achieve a recommended target fibrinogen plasma level dependent on the bleeding type (minor or major). Target level and achieved level after individual dosing as well as the difference between target level and achieved level will be summarized using descriptive statistics and displayed graphically.

The dose of the IMP used per day and in total will be summarised using descriptive statistics for minor and major bleeding events. Frequency of infusions and duration of treatment will also be summarised. The frequency of unscheduled infusions will be summarised descriptively.

9.5 Handling of Missing Data

In general, if not stated differently, missing data will not be imputed.

If the haemostatic efficacy assessment is missing, it will be set to 'none' in the ITT analysis. Subjects with missing haemostatic efficacy assessment will be excluded from the PP population.

Missing MCF and IVR values will not be replaced.

9.6 Randomisation

Not applicable.

9.7 Interim Analysis

An interim analysis will be performed after the data is available for the first bleeding episode of 10 subjects; 2 of these subjects should be between 12 and 18 years old. Results will be included in the submission for registration. Descriptive efficacy and safety analysis will be performed and presented to IDMEAC.

10 ETHICAL, REGULATORY, LEGAL AND ADMINISTRATIVE ASPECTS

10.1 Ethical and Regulatory Framework

This study will be conducted in accordance with the ethical principles laid down in the Declaration of Helsinki. The study protocol and any subsequent amendment(s) will be submitted to an IEC/IRB and to the Regulatory Authority. The study will be conducted in compliance with the protocol, GCP regulations and applicable regulatory requirements.

The regulatory application or submission for regulatory approval will be made by the Sponsor or designated third party (e.g., CRO), as required by national law.

10.2 Approval of Study Documents

The study protocol, a sample of the subject information and informed consent form, any other materials provided to the subjects, and further requested information will be submitted by the Sponsor or the investigator to the appropriate IEC/IRB and the Regulatory Authority. The study approval letter must be available before any subject is exposed to a study-related procedure.

The Sponsor, the investigator and any third party (e.g., CRO) involved in obtaining approval, must inform each other in writing that all ethical and legal requirements have been met before the first subject is enrolled in the study.

